16.2.3. Dose Expansion

16.2.3.1. Every 3 Weeks Dosing Schedule for Multiple Myeloma

Time and Events Table for Full Study (Cycle = 21 days)									
Study Assessments ¹	Screen ²	Day 1 C1	Day 8 C1	Day 15 C1	Day 1 C2	D1 of C3-C16	End of Study Treatment ³⁴	Monthly Follow up ³⁵	
Baseline Demographics	X								
Medical History	X								
Physical Exam	X	X			X	At the start of each cycle	X		
Ocular Exam	X ³				X ⁴	At the start of each cycle ⁴	X ⁴	X ³⁵	
ECOG Performance Status	X				X	At the start of each cycle	X		
Vital Signs (BP, HR, Body Temperature)	X	X ⁵	X	X	X ⁵	At the start of each cycle ⁵	X		
Weight and Height	X	Weight only			Weight only	Weight only - At the start of each cycle	Weight only		
Hematology	X	X ⁶	X	X	X	At the start of each cycle	X		
Clinical chemistry	X	X ⁶	X	X	X	At the start of each cycle	X		
Urine Dipstick	X	X ⁶			X	At the start of each cycle	X		
INR, PTT	X	X ⁶	X	X	X	At the start of each cycle			
HBV/HCV tests	X								
CK-MB , Troponin	X ^{7,8}		X ^{7,8}		X ^{7,8}	At the start of each cycle ^{7, 8}	X ^{7,8}		
BNP	X ⁹								
UPEP and urine Immunofixation	X				X	At the start of each cycle			
SPEP and serum immunofixation and Serum M-protein Calculation	X				X	At the start of each cycle			
Kappa, lambda free LC, FLC ratio	X				X	At the start of each cycle			

CONFIDENTIAL

BMA117159

Time and Events Table for Full Study (Cycle = 21 days)									
Study Assessments ¹	Screen ²	Day 1 C1	Day 8 C1	Day 15 C1	Day 1 C2	D1 of C3-C16	End of Study Treatment ³⁴	Monthly Follow up ³⁵	
24 hr urine protein and albumin	X				X	At the start of each cycle			
IgG, IgM, IgA	X				X	At the start of each cycle			
CRP, beta2 microglobulin	X				X	At the start of each cycle			
Pregnancy Test	X ¹⁰					At the start of cycles 5 ¹⁰ , 9 ¹⁰ , 13 ¹⁰	X ¹⁰	X ¹¹	
Chest X-ray	X								
12-lead ECG	X ¹²	X ¹²	X ¹²	X ¹²	X ¹²	At the start of each cycle ¹²	X ¹²		
LVEF and valves assessment (ECHO)	X ¹³					At the start of cycles 4 ¹³ , 9 ¹³	X ¹³		
Extramedullary Plasmacytoma Imaging	X ¹⁴					At the start of cycles 5 ¹⁴ , 9 ¹⁴ , 13 ¹⁴	X ¹⁴		
BM Aspirate (see below for each test required within procedure):									
Disease assessment	X ¹⁵					At the time of Complete Response			
BCMA assessment and PD (flow)	X ¹⁶		X ^{16, 18}						
FISH testing	X ¹⁷								
BM biopsy for disease assessment	X ¹⁹					At the time of CR (disease assessment only)			
Serum (soluble BCMA)		X ²⁰			X ²⁰	Predose at the start of each cycle	X		

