AMT	Amount of GSK2857916 given (in mg)		AMT = ALTDOSE, where PARAMCD=ALTDOSE only on the dosing line. If infusion was stopped early and then restarted, the dosing information will be captured with more than one line. Each line will represent a part of the infusion (for example from start to first interruption and then from restart to end of infusion). AMT will have to be derived separately from restart of infusion until it is stopped. For all other lines use "0"	adex
INFD	Infusion Duration (day)		INFD is the infusion duration and is computed from start and stop time of infusion (in days) (AENDTM-ASTDTM)/60/60/24 This value will only be used on the dosing line. For all other lines use "0" If infusion was stopped early and then restarted, INFD will have to be derived separately from restart of infusion until it is stopped.	adex
INFH	Infusion Duration (h)		INFH is the infusion duration and is computed from start and stop time of infusion (in h) (AENDTM-ASTDTM)/60/60 This value will only be used on the dosing line. For all other lines use "0" If infusion was stopped early and then restarted, INFH will have to be derived separately from restart of infusion until it is stopped.	adex

CONFIDENTIAL

BMA117159

Column Header	Data Item	Codes	Derivation/Comments	Source data set
RATED	Rate of infusion (mg/day)		RATED = AMT/INFD; This value will only be used on the dosing line. For all other lines use "0" If infusion was stopped early and then restarted, RATED will have to be derived separately from restart of infusion until it is stopped.	derived
RATEH	Rate of infusion (mg/h)		RATEH = AMT/INFH This value will only be used on the dosing line. For all other lines use "0" If infusion was stopped early and then restarted, RATEH will have to be derived separately from restart of infusion until it is stopped.	derived
RTFDD	Relative time from start of first infusion on study (day)		$RTFDD = ((ADTM - ASTDTM) / 60 / 60 / 24)$	adpc, adex
RTFDH	Relative time from start of first infusion on study (h)		$RTFDH = ((ADTM - ASTDTM) / 60 / 60)$	adpc, adex
RTLDD	Relative time from start of the most recent infusion on study (h) done prior to the PK sample		For pre-dose samples, RTLDD will be calculated considering the most recent infusion done prior to the sample. For example, the RTLDD for the pre-dose in Cycle 2 will be computed from the start time of infusion in Cycle 1.	adpc

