DOAE	Duration of adverse event (days)		
This variable is for calculating the duration of adverse event following the 1st occurrence of corneal event in TOXTYPE =1
 
 • When CQ01NAM = Corneal Event and AONGO=N and AENDTF= blank, then DOAE = ADURN; • When CQ01NAM = Corneal Event and AONGO = N and AENDTF= Y/M/D, then DOAE = -99; • When CQ01NAM = Corneal Event and AONGO=Y, then DOAE = (LSTCTDT – ASTDT) + 1; • When CQ01NAM = Corneal Event and AONGO=Y, DOAE = -99 ASTDTF is not missing (has alphabet Y/M/D); • When CQ01NAM = Corneal Event and AONGO=Y, DOAE = -99 if LSTCTDT or ASTDT is missing; • When CQ01NAM = missing, then DOAE = 0; 	adae, adsl
DOAECFLCD	DOAE Censoring Flag Code	0 or 1	
When AONGO=N, then DOAECFLCD=0
 
When AONGO=Y, then DOAECFLCD=1
	adae
LNDOAE	Log of duration of adverse event		
LNDOAE = Log(DOAE);
 
When DOAE=-99, LNDOAE =-99;
 
When DOAE=0, LNDOAE=0
	adae
CUMAMTCT	Cumulative dose to TTECORTOX (mg)		
When CORTOX=1,
 
 • For adex.PARAMCD=ALTDLOSE, CUMAMTCT= Cumulative of adex.AVAL till adae.AESTDY • For corneal toxicity that occurred on dosing days, the dose on the corneal toxicity day was not included in the cumulative dose calculation. Here is the code for that: When adae.AESTDY=adex.ASTDY, then CUMAMTCT= Cumulative of adex.AVAL till (adae.AESTDY -1) 
When CORTOX=0,
 
 • CUMAMTCT= AVAL * WEIGHTBL; Get AVAL for adex.PARAMCD=CUMDOSE 	adex. adae
TAAUCCT	Time-average AUC till		The area under the plasma ADC concentration–time curve (AUC) per day	popPK output,

Column Header	Data Item	Codes	Derivation/Comments	Source data set
	TTECORTOX (AUC/day)		(AUC/day) will be derived for each patient using the available ADC dosing information, individual patient clearance values from the population pharmacokinetic model, and the time to the occurrence of the corneal toxicity.	adae
CANCER	Cancer type	0 or 1	0=Multiple Myeloma, 1=BCMA positive Lymphomas If TRT01AN = 12, then CANCER=1, else CANCER=0	adsl
AMT	Amount (in mg) of GSK2857916 given in first cycle		AMT = AVAL when PARAMCD=ALTDOSE and AVISIT= CYCLE 1 DAY 1	adex
IDOSE	GSK2857916 initial cycle dose (mg/kg)	>0	IDOSE=adex.TRT01A; strip off units	adex
CMAX	First dose Cmax of ADC – model predicted EOI concentration in Cycle 1 (ng/mL)		Individual model predicted conc. at EOI.	PopPK output

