DORD	DOR (Days)		For PARAMCD=DOR_D, AVAL value is assigned to DORD. For subjects where DOR_D is missing, assign "." When TTRCFLCD=0, then DORD = 0	adtte
DORM	DOR (Months)		For PARAMCD=DOR_M, AVAL value is assigned to DORM. For subjects where DOR_M is missing, assign "." When TTRCFLCD=0, then DORM = 0	adtte
DORY	DOR (Years)		For PARAMCD=DOR_D, (AVAL/365) value is assigned to DORY For subjects where DOR_Y is missing, assign "." When TTRCFLCD=0, then DORY = 0	derived
ORDRESP		0,1,2,3,4,5,6	For PARAMCD=BCRSP, assign 0 for PD 1 for SD 2 for MR 3 for PR 4 for VGPR 5 for CR 6 for sCR	adrs
MAXPRED			Obtain AVAL for PARAMCD=MAXPRED. When AVAL is missing, MAXPRED = -999	adrs
RESPRATIO	Transform MAXRED to a ratio to baseline		RESPRATIO = $\max((100+\text{MAXRED})/100, 0.001)$ 
 When MAXRED is missing, MAXRED = -999 and RESPRATIO= -99 When MAXRED is less than -100 e.g. -100.15, RESPRATIO = negative (It is negative but greater than -8.99), then update RESPRATIO = 0.001 When MAXRED is equal to -100, RESPRATIO = 0, then update RESPRATIO = 0.001 	adrs,derived
RSPTYP	Response Type	1,2,3	1 for Serum M-Protein 2 for Serum FLC	adrs

Column Header	Data Item	Codes	Derivation/Comments	Source data set
			3 for Urine M-Protein	
CUMAMTP	Cumulative dose to progression (mg)		
This is needed to derive Time-average AUC till progression. For adtte.PARAMCD=PFS_D, adex.PARAMCD=ALTDOSE, CUMAMTP= Cumulative of adex.AVAL starting from adtte.STARTDT and ending at adtte.ADT
 
For progression that occurred on dosing days, the dose on the progression day was not included in the cumulative dose calculation. Here is the code for that: When adtte.ADT = adex.ASTDT at the last dose for that subject, then CUMAMTCT= Cumulative of adex.AVAL starting from adtte.STARTDT and ending at (adtte.ADT -1)
	adex, adtte
TAAUCP	Time-average AUC till progression (AUC/day)		The area under the plasma ADC concentration–time curve (AUC) per day (AUC/day) will be derived for each patient using the available ADC dosing information, individual patient clearance values from the population pharmacokinetic model, and the time to the occurrence of the PFS	popPK output, adtte

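### Cumulative dose in the corneal exposure-response dataset comes from a different dose source in subjects with and without a corneal event, so an error confined to non-event subjects is possible

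*SAP*

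**What the plan says.** The dataset specification for corneal events in SAP section 16.10.1 defines CUMAMTCT, in mg, as the dose accumulated up to TTECORTOX. The derivation branches on CORTOX.

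- **Event (CORTOX=1):** "For adex.PARAMCD=ALTDLOSE, CUMAMTCT= Cumulative of adex.AVAL till adae.AESTDY". The parameter code is evidently a misprint of ALTDOSE, which section 16.9.1 uses for the milligrams given at each dose. When the event starts on a dosing day, "the dose on the corneal toxicity day was not included in the cumulative dose calculation".
- **No event (CORTOX=0):** "CUMAMTCT= AVAL * WEIGHTBL; Get AVAL for adex.PARAMCD=CUMDOSE".

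No reason is given for changing the dose source. CORTOX is also the outcome that section 16.10.2.1.1 models by logistic regression.

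The efficacy dataset in the same section handles its two cumulative doses as follows:

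- For CUMAMTP (dose to progression), the rule is "CUMAMTP= Cumulative of adex.AVAL starting from adtte.STARTDT and ending at adtte.ADT", with ALTDOSE as the parameter and no branch on event status.
- CUMAMTR (dose to response) does branch. Responders get the ALTDOSE sum and non-responders are assigned TOTAMT.

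The expansion schedule for myeloma in section 16.2.3.1 has weight measured repeatedly ("Weight only - At the start of each cycle"). The PopPK dataset in section 16.9.1 carries a time-varying weight alongside the baseline weight.

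**The concern.** An exposure variable should be measured in the same way in cases and non-cases. Here the outcome decides which dose records are used. If the two sources disagree, the disagreement sits entirely in one outcome group. It is then differential measurement error, not noise shared by both groups.

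The direction would depend on the weight trend. Suppose infused milligrams follow current weight. If weight falls on treatment, the baseline-weight formula overstates dose only in subjects without a corneal event, which would flatten an exposure-toxicity slope. If weight rises, the effect reverses. Section 16.10.2.1.1 also groups exposure into quartiles and quintiles for the severity model, so subjects near a cut-point could change category.

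**Working it through.** The SAP states no figure on this point, so there is none to reproduce. The check compares the two formulas for the same subject.

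**Inputs from the SAP**

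- ALTDOSE is milligrams given (section 16.9.1, AMT row). The corneal dataset also takes its first-cycle AMT from ALTDOSE for every subject, so milligram records exist for non-event subjects.
- CUMDOSE has no unit in the CUMAMTCT row. Section 16.6.2 defines dose intensity as cumulative dose divided by number of cycles, and the dose-intensity tables in section 16.12.4 give it in mg/kg/cycle. Cumulative dose is therefore in mg/kg. Multiplying by weight to reach mg fits this.
- The expansion dose is 3.4 mg/kg (section 5.1).

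**Assumptions, not in the SAP:** baseline weight 80 kg; 8 doses; weight changing linearly from first to last dose; each milligram dose calculated from current weight.

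**Formulas**

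- Milligrams given = 3.4 × 8 × mean weight over the doses. With linear change, the mean is the average of first and last weight.
- CORTOX=0 formula = 3.4 × 8 × baseline weight = 27.2 × 80 = 2176.0 mg.
- Relative error = baseline weight / mean weight − 1.

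| Weight, first to last dose | Mean weight | Milligrams given | CORTOX=0 formula | Error |
|---|---|---|---|---|
| 80 to 80 kg | 80 kg | 27.2 × 80 = 2176.0 | 2176.0 | 0 |
| 80 to 76 kg (5% loss) | 78 kg | 27.2 × 78 = 2121.6 | 2176.0 | +2.6% |
| 80 to 72 kg (10% loss) | 76 kg | 27.2 × 76 = 2067.2 | 2176.0 | +5.3% |
| 80 to 88 kg (10% gain) | 84 kg | 27.2 × 84 = 2284.8 | 2176.0 | −4.8% |

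Dose level, number of doses and starting weight cancel from the ratio. A run with 75 kg and 4, 8 or 16 cycles gave the same percentages for the two losses.

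**When the error is zero.** The formulas agree exactly in two cases:

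1. Milligrams were always set from baseline weight.
2. The mg/kg values were obtained by dividing milligrams given by baseline weight, so that multiplying by that weight returns the milligrams.

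The SAP says only that cumulative dose is the sum over cycles (section 16.6.2) and takes the actual mg/kg dose directly from the exposure dataset (section 16.9.1). It neither states nor excludes either case.

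**What the error can reach.** First-dose CMAX, CTAU, AUC and the two cys-mcMMAF measures come from the PopPK output and do not use CUMAMTCT. The row for TAAUCCT, the time-averaged AUC to the corneal event, refers to available dosing information, individual clearance and time to event. It does not name CUMAMTCT. The statement that the cumulative dose is needed for a time-averaged AUC appears in the CUMAMTP and CUMAMTR rows only.

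**The case against.** The strongest reply is that the existence of any error depends on facts the SAP does not give. Scheduling a weight at each cycle does not show that the dose was recalculated from it, and either zero-error case would make the two formulas equivalent. This stands, and the conclusion has to be conditional.

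Second, a reader might infer that the discrepancy passes into TAAUCCT, with a clearance estimated from administered milligrams dividing a dose on another basis. The text does not support that as a fact. For TAAUCCT the link rests on analogy with CUMAMTP.

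Third, a reader might infer that a named model is biased in a known direction. Section 16.10.2.1.1 does not list CUMAMTCT as a predictor; it refers to exposure generally. Starting doses run from 0.03 to 4.6 mg/kg, about 150-fold (4.6 / 0.03 = 153), so a shift of a few percent is small against the spread of exposure.

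Fourth, the efficacy dataset is not a uniformly consistent comparator. CUMAMTP ignores event status, but CUMAMTR also branches on outcome, and TOTAMT has no row of its own in the specification, so its dose source cannot be read there.

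Finally, the exposure-response work is exploratory and reported separately, and departures from the specification are to be documented. Documenting departures does not help here, because the inconsistency is in the specification itself.

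None of this supplies a reason for two dose sources in one variable.

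**Conclusion.** The point holds as a minor specification defect. CUMAMTCT is built from administered milligrams in subjects with a corneal event and from mg/kg times baseline weight in subjects without one. The outcome under study therefore selects the derivation, without a stated reason.

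The consequence is possible, not established. If milligram doses followed current weight and the recorded mg/kg was not back-calculated from baseline weight, CUMAMTCT would be off in non-event subjects only, by the amounts tabulated above. In either zero-error case nothing changes. The conclusion also rests on CUMDOSE being in mg/kg, which is inferred but firmly so.

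This is not a unit error, since both branches end in milligrams. Nor is it a complaint about accumulating to the event in one group and over all treatment in the other; that follows from defining the variable up to TTECORTOX. No primary or secondary endpoint depends on CUMAMTCT.

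**What to change.** In the corneal-events table of section 16.10.1:

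1. For CORTOX=0, define CUMAMTCT as the sum of ALTDOSE milligrams from first dose to TTECORTOX, which for these subjects is the censoring day.
2. Delete the line that multiplies CUMDOSE by WEIGHTBL.
3. Correct the misprinted code ALTDLOSE to ALTDOSE in the CORTOX=1 branch.

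The cost is about one line of specification and a rerun of one derived variable, from records already used for every dose in the PopPK dataset. If the two sources agree, no value changes. If they do not, the change removes a measurement difference tied to the outcome.

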7.3.1.2.3. Duration of Response

Duration of Response (DOR) is defined, for subjects with a confirmed response (PR or better) as the time between first documented evidence of confirmed response and disease progression or death due to PD, whichever occurs first.

- Duration of response is derived for patients with a confirmed PR or better only.
- Censoring rules will follow those of the TTP analysis.

DOR will be summarized using Kaplan-Meier curves. If there are a sufficient number of progressions or death due to PD among the responders, median DOR, first and third quartiles and 95% CI, will be estimated using the Brookmeyer-Crowley method [Brookmeyer, 1982]. A figure and listing of DOR time will also be provided. Summary and figure of DOR will be based on Part 2 MM population and subgroup: prior anti-cancer therapy of interest; listing of DOR will be based on All Treated MM population.

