BSTAGE	Stage at Screening	1 = I 2 = II 3 = III 4 =	When addc.PARAMCD = STAGESCR and AVALC = I, then BSTAGE = 1 When addc.PARAMCD = STAGESCR and AVALC = II, then BSTAGE = 2 When addc.PARAMCD = STAGESCR and AVALC = III, then BSTAGE = 3 When addc.PARAMCD = STAGESCR and AVALC = UNKNOWN or missing , then	addc

Column Header	Data Item	Codes	Derivation/Comments	Source data set
		UNKNOWN or missing	BSTAGE = 4 Fill on all rows	

For efficacy

General Description:

1. The dataset is sorted by SUBJID
2. Three significant figures for all values except those variables which are integers.
3. Only subjects with CANCER=0 will be included in this dataset as the data for the lymphoma patients will not be fully cleaned at the time of the database cut in 4Q2018.

Column Header	Data Item	Codes	Derivation/Comments	Source data set
C	Line number/exclusion identifier	Row Number	Set to line/row number	
STUDY	Study ID		1 = BMA117159	adsl
SUBJID	Subject identifier from source data		SUBJID = SUBJID	adsl
ID	NONMEM subject identifier		Sequential subject identifier across studies after data is sorted by SUBJID. Starting with P	derived
PFSCFLCD	PFS Censoring Flag Code	0 or 1	For PARAMCD=PFS_D, CNSR value is assigned to PFSCFLCD 0=Event 1=Censor	adtte
PFSD	PFS (Days)		For PARAMCD=PFS_D, AVAL value is assigned to PFSD When AVAL is missing for PFS_D, then PFSD = -99.	adtte
PFSM	PFS (Months)		For PARAMCD=PFS_M, AVAL value is assigned to PFSM When AVAL is missing for PFS_M, then PFSM = -99.	adtte
PFSY	PFS (Years)		For PARAMCD=PFS_D, (AVAL/365) value is assigned to PFSY When AVAL is missing for PFS_Y, then PFSY = -99.	derived
TTRCFLCD	TTR Censoring Flag Code	0 or 1	For PARAMCD=TTR_D, Assign 1 to TTRCFLCD. For subjects where TTR_D is missing, assign 0 to TTRCFLCD.	adtte
TTRD	TTR (Days)		For PARAMCD=TTR_D, AVAL value is assigned to TTRD. For subjects where TTR_D is missing, assign PFSD to TTRD.	adtte

Column Header	Data Item	Codes	Derivation/Comments	Source data set
TTRM	TTR (Months)		For PARAMCD=TTR_M, AVAL value is assigned to TTRM. For subjects where TTR_M is missing, assign PFSM to TTRM.	adtte
TTRY	TTR (Years)		For PARAMCD=TTR_D, (AVAL/365) value is assigned to TTRY. For subjects where TTR_D is missing, assign PFSY to TTRY.	derived
DORCFLCD	DOR Censoring Flag Code	0 or 1	For PARAMCD=DOR_D, CNSR value is assigned to DORCFLCD 0=Event 1=Censor Assign "." for missing.	adtte

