16.10.2.1.2. Clinical Response

Presence or absence of clinical response will be described using a conventional logistic regression model. Time to response will be explored using Kaplan Meier plots categorized by exposure measures.

PFS will be explored using Kaplan Meier plots categorized by exposure measures and occurrence of progression may also be described using a conventional logistic regression model.

Duration of response will be explored using Kaplan Meier plots categorized by exposure measures.

Best clinical response will be analyzed using an ordered logistic regression, with response categorized from 0 (progressive disease) to 6 (stringent complete response). Exposure will be treated as a categorical variable subdivided into quartiles and quintiles.

In the ordered logistic regression analyses, the use of categorical measures of exposure in lieu of continuous variables will allow for non-parametric descriptions of response functions.

Best clinical response as assessed by maximum reduction in M-protein or FLC will be analyzed by exposure (continuous and/or categorized by exposure measures).

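### In the exploratory efficacy exposure-response dataset, the time-to-response censoring flag is coded as an event indicator without a legend, and non-responders' duration of response is specified as both missing and 0

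*SAP*

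**What the plan says.** The efficacy part of SAP section 16.10.1 specifies the file for the exposure-response analyses of efficacy. It contains three variables labelled as censoring flags.

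- PFSCFLCD: "For PARAMCD=PFS_D, CNSR value is assigned to PFSCFLCD 0=Event 1=Censor". DORCFLCD takes its CNSR value in the same way, with the same legend, and is left missing where there is no DOR record.
- TTRCFLCD carries the label "TTR Censoring Flag Code" and the rule "For PARAMCD=TTR_D, Assign 1 to TTRCFLCD. For subjects where TTR_D is missing, assign 0 to TTRCFLCD". It has no 0/1 legend. Subjects without a response time receive their PFS time as TTRD.

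The corneal table in the same section has a fourth such flag, for event duration: "When AONGO=Y, then DOAECFLCD=1", with 0 for events that are not ongoing.

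The DORD row first sets the value to missing where no DOR record exists, and then adds: "When TTRCFLCD=0, then DORD = 0". DORM and DORY follow the same pattern. The main definition, in section 7.3.1.2.3, is narrower: "Duration of response is derived for patients with a confirmed PR or better only".

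Section 16.10.2.1.2 states the use: "Time to response will be explored using Kaplan Meier plots categorized by exposure measures". It plans the same kind of plot for duration of response and does not restate a restriction to responders.

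**The concern.** In one table, three variables share a label and a naming pattern, and one of them runs in the opposite direction. Under section 16.5.3 the file goes as a CSV to the modelling and simulation function, which analyses and reports it separately (section 16.10.2). An analyst who sets one censoring value for all the flags would treat every responder as censored and every non-responder as responding on the PFS date. The comparison of response between exposure groups would then reverse.

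The DOR columns raise a different problem. Non-responders satisfy both instructions in the cell, so the specification gives two values for the same row. If the rules run in the order written, 0 replaces missing, and subjects with no response to time carry a numeric duration. Any analysis that includes those zeros mixes response rate with duration among responders.

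**Working it through.** The plan gives no figure to reproduce here. The check is a comparison of coding rules, followed by what each misuse would do.

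**1. Flag direction (all from section 16.10.1)**

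| Flag | Table | Event | No event | Legend |
|---|---|---|---|---|
| PFSCFLCD | efficacy | 0 | 1 | yes |
| DORCFLCD | efficacy | 0 | 1 (missing if no DOR record) | yes |
| DOAECFLCD | corneal | 0 (not ongoing) | 1 (ongoing) | rule only |
| TTRCFLCD | efficacy | 1 (response time exists) | 0 (no response time; PFS time used) | rule only |

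Giving PFS time to subjects with TTRCFLCD=0 makes sense only if 0 means censored without response. The CUMAMTR row confirms this: it explains TTRCFLCD=0 as subjects who had no response. TTRCFLCD is therefore an event indicator under a censoring label.

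**2. If TTRCFLCD is read with the PFS/DOR legend**

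Let p be the share of subjects with a response. The correct event share is p; the misread share is 1 − p. The documents give no p by exposure group, so these values are assumptions:

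- p = 20%: read as 80%
- p = 40%: read as 60%
- p = 60%: read as 40%

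If p is larger in one exposure group than in another, 1 − p is smaller, so the order of the groups reverses.

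**3. The two DOR instructions**

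A non-responder has no DOR record, so the first rule gives missing. The same subject has TTRCFLCD=0, so the second rule gives 0. DORCFLCD stays missing. The row then holds a duration of 0 with no event status.

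**4. What the zeros do, by use**

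- *Kaplan-Meier with DORCFLCD, missing flag dropped:* non-responders leave the analysis and the estimate is the responder-only one.
- *Zeros censored at day 0:* they leave the risk set before any positive duration, so the curve is unchanged.
- *Missing flag read as 0 = event:* survival just after day 0 is 1 − (1 − p) = p, so the median is 0 when p is 50% or less.
- *Plain mean over all rows:* p × (mean among responders).

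An illustration with invented inputs shows the range. Responder durations are spread evenly over 30 to 360 days, mean (30 + 360)/2 = 195, about 60% of them events, in a file of 40 subjects. That size was chosen for convenience and is not the size of this dataset.

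| p | Median, dropped or censored | Median, zeros as events | Mean with zeros |
|---|---|---|---|
| 20% | about 266 days | 0 | 0.2 × 195 = 39 |
| 40% | 250 days | 0 | 0.4 × 195 = 78 |
| 60% | about 260 days | about 102 days | 0.6 × 195 = 117 |

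The planned use, Kaplan-Meier with DORCFLCD, falls under the first case unless the missing flag is filled in.

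**The case against.** The case on the other side is strong on consequences. TTRCFLCD is fully defined: each value has an explicit rule, the time given to flag-0 subjects fits only one meaning, and the CUMAMTR row states that meaning. No sentence imposes one convention on all flags. The corneal table also pairs a time with an indicator that is 1 for an event (CORTOX with TTECORTOX), so the coding itself is not unusual. This stands: a careful reader will decode the flag. What remains is the wrong label and the absent legend.

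For DOR, the only exposure-response analysis named is Kaplan-Meier, which needs an event status, and non-responders have none. The 0 also resembles a placeholder, since the corneal table sets duration to 0 for subjects with no event. This stands as well. It does not explain why one cell prescribes two values, or why either should be numeric when section 7.3.1.2.3 derives DOR for responders only.

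A reader might infer that DOR in this dataset is corrupted, or that its median will be 0. The documents do not support that. It requires the missing DORCFLCD to be treated as an event, or the zeros to be used without the flag, and the SAP prescribes neither. Counts of swapped subjects built on the Part 2 myeloma cohort of up to 40 and a 40% response rate would not describe this file either. It holds every myeloma subject, including Part 1 at 0.03 to 4.6 mg/kg, and 40% is the edge of the alternative hypothesis for the expansion cohort.

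**Conclusion.** Two specification defects hold. TTRCFLCD is labelled a censoring flag but coded as an event indicator, opposite to the stated legend of PFSCFLCD and DORCFLCD and with no legend of its own. DORD, DORM and DORY prescribe both missing and 0 for non-responders, against the responder-only definition.

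The first creates a risk of turning a response share p into 1 − p in the time-to-response plots; a swap is not certain, because the correct reading can be recovered from the same section. The second distorts results only under the two misuses named above.

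The point is minor. The analyses are exploratory and reported separately. The main summaries in sections 7.3.1.2.3 and 7.3.1.2.4 have their own definitions and do not read these columns. Section 16.10.1 also requires deviations between specification and final dataset to be documented. The conclusion rests on the coding rules alone; the percentages and days in the working are illustrations.

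**What to change.** For the flag, choose one of two routes.

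- Rename TTRCFLCD as a response indicator and add the legend 1 = response, 0 = no response (censored at PFS time). The CUMAMTR condition then needs no change of logic, only the new name. This is the simpler route.
- Keep the censoring label, recode to 0 = event and 1 = censored, state that legend, and change every condition that tests TTRCFLCD in the same edit: DORD, DORM, DORY and CUMAMTR. A partial change would be worse than none. Left as they are, those rules would overwrite responders' real durations with 0 and set their cumulative dose to response to the total dose, which feeds the time-averaged AUC to response (TAAUCR).

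On either route, delete the lines that set DORD, DORM and DORY to 0 when TTRCFLCD=0. Non-responders then stay missing and out of all DOR analyses, in line with section 7.3.1.2.3.

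The cost is a few lines of specification and code. No new data are needed.
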